**Study Title:** Impact of Decision Aids in Urogynecology

**Document Title:** Design and Analysis plan for a study examining the impact of decision aids in Urogynecology

**PI:** [name] ([[contact]](mailto:[contact]))

**Statistician:** [name]

**Co-Investigators and Study team:** [name] (MGH), [name] (MGH), [name] (MGH), [name] (MGH)

**ClinicalTrials.gov:** NCT04369404

**Date:** June 5, 2023

*Background:*

Pelvic floor disorders including pelvic organ prolapse (POP), stress urinary incontinence (SUI), and overactive bladder (OAB) are significant source of impaired quality of life, psychosocial distress, and financial burden. Patients with these conditions broadly desire symptom improvement and a better understanding of their condition and treatment options.

*Purpose:*

To examine the efficacy and acceptability of decision aids (DAs) in counseling urogynecology patients with prolapse, stress urinary incontinence, or refractory overactive bladder.

*Design*

A before-after study first enrolled patients into a control group that underwent usual care without a DA. Then, the study enrolled patients in the intervention group, where providers utilized a DA for counseling. Post-visit patient surveys assessed treatment preference, knowledge, and patient-physician collaboration using SURE, CollaboRATE, and Shared Decision Making (SM) Process scales. Post-visit provider surveys assessed perception of the decision-making process and visit length. Independent t-tests were used for continuous variables (Knowledge and SDM Process scores) and Chi-square for categorical variables (treatment preference, SURE, and CollaboRATE).

*Materials:*

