The three decision aids used for this study focused on POP, SUI, and OAB. The DAs were created by the Health Decision Sciences Center (HDSC) and Female Pelvic Medicine and Reconstructive Surgery (FPMRS0 faculty at Massachusetts General Hospital (MGH). These DAs were reviewed by experts at the Blum Family and Learning Center at MGH for plain language and clarity. The DA worksheets are short, paper-based forms designed to support SDM in a clinical encounter to present treatment options, and to discuss risks and benefits of each treatment option. The main feature of these one-page worksheets is the decision matrix in the middle of the page, listing four common treatment options down the left-hand side, as well as a brief explanation of the treatments' benefits, risks, and next steps. This format allows patients to visually see the pros and cons of each treatment and allows them to select an option that most closely aligns with their values.

*Sample:*

We conducted a before-after pilot study enrolling patients from the FPMRS division of the Obstetrics and Gynecology department at MGH, located in Boston, Massachusetts. Eligible patients were 18-95 years old, with POP, SUI, or OAB, and preferred language English. Patients were ineligible if they had prior surgery for POP or incontinence or if they did not attend the visit.

*Intervention:*

The intervention group, providers had access to the DA worksheets for their routine office visits and utilized the DA with the patient. In the control arm, the providers did not utilize the DAs.

*Survey protocol:*

The survey was given between February 2019 and April 2019. Participants were asked if they would be interested in participating in a research study. Then, they reviewed an information sheet that described the study and had to acknowledge that they read it and were willing to continue to the survey. Then, they continued to the survey. They were asked to complete the survey either after the visit in the waiting area or returning it in a self-addressed envelope to the research team.

*Risk and Adverse Events:*

No diagnosis or treatments were offered or administered as part of this study. The standard of care is that physicians discuss appropriate treatment options, including their benefits and risks. There are minimal risks associated with participating in the survey. No confidential or PHI was collected as part of this study.

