- *SDM Process scale:* A four-item measure that assess discussion of options, pros, cons, and preferences. A total score is calculated according to established scoring guides and ranges from 0-4, with higher scores indicating more shared decision making. Scores have been related to increased patient satisfaction with treatment outcomes and current symptoms, decreased decisional regret, and higher quality of life and symptoms scores.

*Provider Post-Visit Surveys:* Assessed clinicians' perceptions of patient knowledge, involvement in the decision-making process, length of visit, perception of patient satisfaction, and each provider's own satisfaction with the visit.

*Sample Size:* There was no formal power calculation done for this pilot study.

*Statistical Methods:*

This pilot study assessed the feasibility of incorporating DAs into the clinical visit and differences in the decision-making metrics between the groups. We examined efficacy by comparing the intervention and control groups on measures of knowledge scores, SURE top cores, CollaboRATE top scores. We examined acceptability of the intervention by looking at the usage of the DAs, clinicians' satisfaction with the visit, and perceptions of length of visit. Differences between cohorts were examined using independent t-test (2-sided) for continuous variables and Fisher's Exact (2-sided) test for categorical variables. The data from the intervention group was analyzed with an intention-to-treat analysis.

*Data Sharing:*

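### Does describing the intervention group by decision aid use undo the intention-to-treat analysis and leave decision aid usage unmeasurable?

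*Combined protocol and SAP*

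**What the plan says.** The Design section describes two cohorts enrolled one after the other: "A before-after study first enrolled patients into a control group that underwent usual care without a DA". It continues: "Then, the study enrolled patients in the intervention group, where providers utilized a DA for counseling". The Intervention section joins access and use: "The intervention group, providers had access to the DA worksheets for their routine office visits and utilized the DA with the patient". It describes the control arm by the absence of DA use.

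The Statistical Methods section then says: "The data from the intervention group was analyzed with an intention-to-treat analysis". It also makes usage an outcome: "We examined acceptability of the intervention by looking at the usage of the DAs", alongside clinician satisfaction and perceived visit length.

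The listed patient measures are knowledge, treatment preference, SURE, CollaboRATE and SDM Process. The provider survey is summarised in one sentence, covering "perceptions of patient knowledge, involvement in the decision-making process, length of visit" and two satisfaction items. Neither list has an item on whether a DA was used.

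**The concern.** Two sections present DA use as a property of the intervention group. If use were the condition for membership, a visit in the DA period without a DA would belong to neither group. Intention-to-treat would then add nothing, and usage would be 100% by definition, although the Statistical Methods section treats it as something to examine.

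The allocation is not randomised, so this could matter. If clinicians chose which visits received the DA and only those visits were analysed, a selected group would be compared with an earlier cohort to which no such selection applied. Part of any difference could then reflect which patients were chosen.

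The usage outcome looked exposed as well. It is one of three acceptability measures and bears directly on the feasibility aim, yet the plan names no item, log, definition or denominator for it. The intention-to-treat label also seemed to claim more than an analysis of survey respondents can give.

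**Working it through.** The plan has no figure to reproduce: Sample Size states that no power calculation was done, and no usage rate, effect size or number of patients is given. The check is mainly a comparison of texts.

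**1. What places a patient in a cohort?**

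- Design: order of enrolment, control first and intervention second.
- Intervention: access to the worksheets, then use.
- Sample: the stated grounds for ineligibility are prior surgery for prolapse or incontinence and not attending the visit. Non-use of the DA is not among them.
- No section moves a patient between groups according to use.

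The only operating rule is the period of enrolment. The statements about use fit as a description of the intended intervention.

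**2. Which reading makes the Statistical Methods section coherent?**

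| Reading | Intention-to-treat sentence | Usage outcome |
|---|---|---|
| Membership by use | Has no content | Fixed at 100% |
| Membership by period | Keeps non-use visits | Can vary from 0 to 100% |

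Only the second reading gives both statements a function. An analyst following the section as written would keep every DA-period respondent in the intervention group.

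**3. Is usage without data?** The survey forms are not reproduced. Data Sharing refers to surveys and data dictionaries as separate materials available to interested investigators, and Statistical Methods says in the past tense that usage was examined. The document therefore leaves the source unstated. It does not show that there was none.

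**4. How far apart could the two readings be?** Let *u* be the proportion of DA-period visits with the DA used and *E* the effect among users, with no effect in non-users. The period-based difference is *u* × *E*, the users-only difference is *E* (before any selection), and the gap is (1 − *u*) × *E*. With *E* assumed to be 20 points:

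| *u* | Period-based | Users only | Gap |
|---|---|---|---|
| 0.6 | 0.6 × 20 = 12 | 20 | 8 |
| 0.7 | 0.7 × 20 = 14 | 20 | 6 |
| 0.8 | 0.8 × 20 = 16 | 20 | 4 |
| 0.9 | 0.9 × 20 = 18 | 20 | 2 |
| 1.0 | 1.0 × 20 = 20 | 20 | 0 |

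On a standardised scale, an assumed 0.5 SD effect in users becomes 0.8 × 0.5 = 0.40 SD at 80% usage. Every input here is assumed. The tables show that the choice of reading can matter, but they do not place this study anywhere in the range.

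**The case for a change.** The strongest case for acting is that the contradiction is on the page and cheap to remove. Two sections state use as fact, a third needs use to vary, and nothing says how a DA-period visit without a DA is handled. A data set is to be shared, so outside users would benefit from a clear definition of the intervention group. Aligning the wording needs no new data.

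The wording is indeed loose, and the plan does not state the source, definition or denominator for usage. Anyone reporting that outcome has to supply them. It is also true that results come from respondents, some of whom could return the form by post, and that the knowledge score requires at least half the items. That is a question of non-response, separate from how the group is defined, and the half-items rule is stated for all respondents, so it applies to both cohorts.

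The stronger claims do not stand. The document does not make use the criterion for membership, does not say that clinicians selected visits for the DA, and does not show that usage could not be estimated. Adding a yes/no item on DA use to the provider survey is no longer possible: surveys were given in February to April 2019, and the document is dated June 5, 2023.

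**Conclusion.** The concern does not call for a change. Cohort membership follows the enrolment period, and the intention-to-treat sentence directs that intervention-period visits be kept whether or not the DA was used. That is already the cohort a careful analyst would choose. The statements about use in the Design and Intervention sections are a looseness of description, and the missing detail on usage is a gap that the study team can fill from its own forms and records when it reports the result.

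No size can be attached for this study. The gap of 2 to 8 points rests wholly on an assumed 20-point effect in users, none in non-users, and usage of 90% to 60%; it vanishes at full usage. The conclusion rests on reading the before-after design as the rule for membership, which the text supports and nothing in it contradicts. It would change if there were evidence that DA-period patients were dropped or reclassified for non-use; the document contains none.
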